10 IDENTIFICATION AND ACCESS TO SOURCE DATA

10.1 Web-Based Data Collection and Management System

Data collection will occur via a web-based data entry system to allow easy access to enrollment 24 hours a day, 7 days a week. Upon enrollment, a form submission schedule is generated for each subject and displayed as a grid of forms by study visit that permits direct access to each electronic CRF for data entry. As data are entered, they are validated through range and within-form consistency checks. The investigator must ensure that all web-based CRFs are completed in a timely fashion for each subject in the study.

10.2 Certification in the Use of Web-Based Data Entry System

The clinic and laboratory staff will be trained in the use of the data entry and specimen-tracking systems. Once certified, users are permitted to enter data into the production system. Access is password controlled. Certification for use of the web-based data entry system will be completed via telephone and/or web-cast training.

10.3 Data Management

Information regarding the subject's history, laboratory tests, nutritional intake, evaluation of allergic response and follow-up status will be stored and processed through the data center. Quality control procedures and a feedback system between the data center and the sites will be instituted to ensure the accuracy and completeness of the data collected.

10.4 Access to Data

The investigational sites shall periodically permit authorized representatives of the Study sponsor, and/or regulatory health authorities to examine clinical records and other source documents for the purpose of safety monitoring, quality assurance reviews, audits and evaluation of the study progress throughout the entire study period. The investigator is required by law and applicable guideline (21 CFR 312.62, EU Clinical Trials Directive 2001/20/EC and ICH E6) to keep accurate case records for at least 2 years after the last approval of a marketing application in an ICH region and until there are no pending or contemplated marketing application in an ICH

region. These documents should be retained for a longer period however if required by the applicable local regulatory requirements or by an agreement with the sponsor.

11 QUALITY CONTROL AND QUALITY ASSURANCE

11.1 Statement of Compliance

This study will be conducted using good clinical practice (GCP), as delineated in the United States Code of Federal Regulations (CFR) – 21 CFR Parts 50, 54, 56 and 312 and in the International Council for Harmonisation of Technical Requirements for Pharmaceuticals for Human Use (ICH) "Guidance for Industry: E6 Good Clinical Practice Consolidated Guidance", and according to the criteria specified in this study protocol. Before study initiation, the protocol and the informed consent documents will be reviewed and approved by an appropriate IRB/EC and other applicable health authorities. Any amendments to the protocol must also be approved by Aimmune Therapeutics, IRB/EC and other applicable health authorities before they are implemented. Any amendments to the consent materials must also be approved by Aimmune Therapeutics and IRB/EC before they are implemented.

11.2 Informed Consent/Assent

The informed consent/assent form is a means of providing information about the study to a prospective adult subject or a pediatric subject's parent/guardian and allows for an informed decision about participation in the study. Because the study population will comprise a significant percentage of children, parents or legal guardians will be asked to read, sign and date a consent form before a child enters the study, takes study product, or undergoes any study-specific procedures. Children will sign an assent as appropriate. Consent materials for parents/guardians who do not speak or read English will be translated into the appropriate language. The informed consent/assent form will be evaluated for revision whenever the protocol is amended. A copy of the informed consent/assent will be given to a prospective adult subject or a pediatric subjects' parent/guardian for review. The investigator (or designee), will review the consent/assent and answer questions, as well as emphasize the need to avoid allergen exposure other than to AR101, and the necessity to continue exposure to AR101 to maintain desensitization. The prospective adult subject or a pediatric subject's parent/guardian will be told that being in the study is voluntary and that he or she may withdraw his/her child from the study at any time, for any reason.

In the optional saliva substudy (**North America sites only**) in which samples will be obtained noninvasively from ARC003 participants, only subjects enrolled in ARC003 and providing additional consent for this substudy are eligible to participate (**Appendix 6**).

11.3 Privacy and Confidentiality

A subject's privacy and confidentiality will be respected throughout the study. Each subject will be assigned a sequential identification number and these numbers rather than names will be used to collect, store and report subject information.

12 RESOURCE SHARING

All data derived from this study will be sent to the Reporting Center for storage and analysis. Subject data will be anonymized to maintain subject confidentiality. All data derived from these studies will be published in peer-reviewed scientific journals in a timely manner. The sponsor will review all manuscripts prior to submission to journals for publication and all abstracts prior to submission to national and international meetings. All data sets will be archived by the Reporting Center and may be made available to interested, outside investigators with the approval by the sponsor.

13 PROTOCOL DEVIATIONS

The investigators and site staff will conduct the study in accordance to the protocol. Any change, divergence, or departure from the study design or procedures constitutes a protocol deviation. Whenever applicable, corrective actions will be developed by the site and implemented promptly as a result of protocol deviations.

13.1 Major Protocol Deviation (Protocol Violation)

A Protocol Violation is a deviation from the IRB approved protocol that may affect the subject's rights, safety, or well-being and/or the completeness, accuracy and reliability of the study data. In addition, protocol violations include willful or knowing breaches of human subject protection regulations, or policies, any action that is inconsistent with medical, and ethical principles, and a serious or continuing noncompliance with federal, state, local or institutional human subject protection regulations, policies, or procedures.

13.2 Nonmajor Protocol Deviation

A nonmajor protocol deviation is any change, divergence, or departure from the study design or procedures of a research protocol that does not have a major impact on the subject's rights, safety or well-being, or the completeness, accuracy and reliability of the study data.

13.3 Reporting and Managing Protocol Deviations

Non-major protocol deviations related to data entry or visit adherence are captured within the data system and are not additionally reported on a separate CRF.

The study site Principal Investigator has the responsibility to identify, document and report protocol violations/deviations and appropriate corrective action plans which are described above. However, protocol violations/deviations may also be identified during site monitoring visits or during other forms of study conduct review. All protocol violations will be reported in the data system on a specific CRF.

Appendix 1: Schedule of Events

					Up-dosing Period			Maintenance Period		
	Visit	Screening/ Baseline	Initial Escalation		CRC Dosing	Interim (80 mg) Visit	End of Period (300 mg) Visit	CRC Dosing	Exit/Early Discontinuation Visit	Un- scheduled ^c
			Days 1-2 ^a	5-10 days post- DBPCFC	~every 2 weeks for 20- 40 weeks ^b	Approx. Week 10	≤ Week 40	At 2 wks & every 4 wks thereafter for ~24 wks		
Informe	ed consent/assent	Х								
Inclusio	on/Exclusion	Х								
Medica	l/allergy history	Х								
Diet (fo	od allergen) history	Х	Х		Х	Х	Х	Х	Х	Х
	nitant medications	Х	Х		Х	Х	Х	Х	Х	Х
	l exam ^d	Х	Х		Х	Х	Х	Х	Х	Х
	gns (BP, PR, temp)	X X	Х		X	Х	X	Х	Х	X
	Spirometry (FEV1) or PEFR ^e		Х		Х	Х	Х	Х	X	Х
	Pregnancy test ^f					Urine	Urine		Urine	
-	FAQLQ & FAIM questionnaires								X ^p	
Palatab	Palatability questions								$\mathbf{X}^{\mathbf{q}}$	
TSQM-	TSQM-9 and Exit questionnaire								X ^r	
	Peanut-specific IgE, IgG4 ^g	Х					Х		Х	Х
Blood draw	CBC	Х					Х		Х	Х
ulaw	Optional extra vol. for ITNh	Х					Х		X ⁱ	Х
	Optional saliva collection, and packaging/shipping									
	No GI symptoms (controls) GI symptoms (cases)				$egin{array}{c} \mathbf{X}^{\mathrm{j}} \ \mathbf{X}^{\mathrm{j}} \end{array}$		Х		Х	
Optional additional blood draw for post- DBPCFC ITN sample				X ^k						
Skin prick test		Х					Х		Х	
Administration of OIT at site			Х		Х	Х	Х	Х		Х
Dispens	Dispense / return unused study drug		Х		Х	Х	Х	Х	Х	Х
DBPCFC (2 parts within 7 days)		X ¹							X ^m	
Monitor AEs / allergic symptoms ⁿ		Х	Х		Х	Х	Х	Х	Х	Х
Monito	r for compliance				Х	Х	Х	Х	Х	Х

				Up-dosing Period			Maintenance Period		T
Visit	Screening/ Baseline	Initial Escalation		CRC Dosing	Interim (80 mg) Visit	End of Period (300 mg) Visit	CRC Dosing	Exit/Early Discontinuation Visit	Un- scheduled ^c
		Days 1-2 ^a	5-10 days post- DBPCFC	~every 2 weeks for 20- 40 weeks ^b	Approx. Week 10	≤ Week 40	At 2 wks & every 4 wks thereafter for ~24 wks		
Assessment of Asthma	Х				Х	Х		Х	
Subject reminder to avoid all peanut	Х	X	Х	Х	X	X	X	Х	Х
Telephone Follow-up ^o		Х		Х	Х	Х			Х
PEESS TM v2.0 questionnaire									Xs

Footnotes:

- a) The Initial Escalation Visit will be scheduled within 10 days after the Screening DBPCFC. See **Table 3-1** for dose escalation schedule. Subjects will begin home dosing at dose 3 mg/d.
 - Day-1: Escalation to at least 3 mg or 6 mg, as tolerated (subjects who cannot tolerate 3 mg are escalation failures).

Day-2: Confirm tolerance of 3 mg.

- b) Subjects return to clinic every 2 weeks for up-dosing to a maximum of 300 mg, following the dose escalation schedule in Table 3-2, unless up-dosing is delayed due to allergic reaction.
- c) Any of the procedures performed at CRC Dosing Visits may be performed at Unscheduled Visits.
- d) Physical exam to include height and weight. At the investigator's discretion, symptom-directed physical exams may be completed at up-dosing visits during the Up-dosing Period, and CRC Dosing visits during the Maintenance Period. Full physical exams are to be conducted at the Screening/Baseline, the first 80 mg up-dosing, the first 300 mg up-dosing, and the Exit/Early Discontinuation (Termination) visits.
- e) Peak expiratory flow rate (PEFR): To be conducted prior to any DBPCFC, 3 attempts should be made with the best value recorded. PEFR should be measured at the same time for each visit assessment. If a subject's pulmonary status is in question at any time during the study, performance of pulmonary function testing (spirometry) is suggested.
- f) For females of childbearing potential.
- g) Blood for peanut specific IgE, IgG4 is to be drawn prior to DBPCFC.
- h) Optional blood draw for subjects \geq 30 kg only. No more than 5 mL/kg may be drawn, up to a maximum of 50 mL total; analysis by Immune Tolerance Network (ITN).
- i) Blood draw to be collected prior to the Exit DBPCFC (a second draw, 5-10 days post-DBPCFC, will be collected in ARC004; for subjects not continuing to ARC004, specimen collection should be as an Unscheduled ARC003 visit).
- j) Subjects withdrawing early from ARC003 with GI symptoms who were not already enrolled in the optional saliva substudy will be allowed to enroll upon early termination (North America sites only).
- k) Blood draw to be collected 5-10 days after the Screening DBPCFC.
- 1) Eligible subjects, those who satisfy all other screening requirements, will undergo a DBPCFC at the end of the Screening Period to a maximum challenge dose of 100 mg.
- m) Eligible subjects, those who up-dose to 300 mg and maintain for ~24 weeks, will undergo a DBPCFC at the end of Maintenance Period Visit to a maximum challenge dose of 1000 mg.
- n) AEs will be evaluated from the onset until the event is resolved or medically stable, or until 30 days after the subject completes study treatment, whichever comes first.
- o) Phone calls will occur 1 day after each escalation visit to inquire about allergic symptoms and promote compliance
- p) FAQLQ and FAIM to be filled up prior to screening DBPCFC and after exit DBPCFC and unblinding
- q) Palatability questions to be answered before the exit DBPCFC for all patients
- r) TSQM-9 and Exit questionnaire to be answered after exit DBPCFC and unblinding for all active patients

- s) Subjects under the age of 18 years who fall into any of these 3 categories will be asked to fill out the PEESSTMv2.0 questionnaire (Franciosi et al., 2011), with the assistance of a parent or guardian, as appropriate, every month for 6 months:
 - Any subject whose dose is withheld for > 7 days due to GI AEs and resumes dosing at a reduced dose level (Section 6.7)
 - Any subject who develops chronic/recurrent GI AEs at or before reaching the 20 mg dose level and resumes dosing after a 30-day dosing hiatus (Section 6.7.3.2)
 - Any subject who permanently discontinues dosing who had experienced GI AEs (Section 4.3.2)

Note: BP = blood pressure; PR = pulse rate; temp = body temperature; OIT = oral immunotherapy; DBPCFC = double-blind, placebo-controlled food challenge

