6.2 Screening and Baseline

Screening may occur over several days and will include the following assessments/procedures:

• Informed consent and assent, as age appropriate

- Inclusion/exclusion criteria review
- Medical and allergy history review
- Concomitant medication review
- Diet (food allergen exposure) history review
- Completion of the food allergy related quality of life questionnaire (FAQLQ), and the food allergy independent measure (FAIM) questionnaire. Both questionnaires will be completed before the DBPCFC
- Assessment of asthma control using the Asthma Control Test questionnaire in subjects with asthma
- Physical examination, including weight and height
- Vital sign measurement (blood pressure, pulse rate, body temperature)
- Spirometry (FEV1) and/or Peak Expiratory Flow Rate (PEFR) prior to any DBPCFC; 3 attempts of FEV1 are performed and the best value is taken; 3 attempts of PEFR are to be performed, and the best value taken. PEFR should be measured at the same time for each visit assessment.
- Serum pregnancy test, for females of childbearing potential
- Blood draw to collect samples for:
 - Peanut-specific IgE, component-resolved IgE (including at screening determination of Ara h 1, Ara h 2, Ara h 3, Ara h 8 and Ara h 9) peanut IgE, total IgE, and peanut-specific IgG4 (immunoglobulin assays) The amount of blood to be taken for the immunoglobulin assays will be communicated from the central laboratory and included in the manual of procedures.
 - Complete blood cell count (CBC), obtained with the same venipuncture as the blood draw for the immunoglobulin assays
 - Optional exploratory immune cell characterization by the Immune Tolerance Network (ITN). Note that these samples can be obtained with the same venipuncture as the blood draw for the immunoglobulin assays and CBC, but will require an addition volume of blood to be collected. Separate informed consent is required.

The amount of blood to be taken in total for the above assays (required immunoglobulin assays, required CBC, and optional immune cell characterization assays) will not exceed a total volume of 0.67 mL/kg in children, to a maximum of 50 mL, total, in 8 weeks. Blood draw should be collected in compliance with local laboratory guidelines and testing regulations.

- Skin prick test to peanut extract
- DBPCFC conducted in accordance with PRACTALL guidelines, with assessments made by a Blinded Evaluating Physician (Blinded Assessor), as described in Section 6.6

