6.2.1 Optional Post-DBPCFC Blood Draw Visit

This visit is only for subjects who consent to participate in the optional post-DBPCFC blood draw for exploratory immune cell characterization by the Immune Tolerance Network (ITN).

The visit is to occur 5-10 days after completion of the Screening DBPCFC and may coincide with an Initial Escalation Day Visit (Section 6.3.1).

The only procedure performed on this day is a blood draw. The amount of blood to be taken for the immune cell characterization assays will be provided in the manual of procedures and will be such that it will not cause the total blood volume collected to exceed 0.67 mL/kg in children, or maximum of 50 mL, total, in 8 weeks. Blood draw should be collected in compliance with local laboratory guidelines and testing regulations.

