6.3.4 End of Up-dosing / Start of Maintenance Period Visit

The first 300 mg in-clinic dosing visit is the end of the Up-dosing Period; it is also the start of the Maintenance Period. At this visit the following procedures are to be performed in addition to those performed at the up-dosing visits:

- Complete (not just symptom-directed) physical examination, including height and weight
- Assessment of asthma control in asthmatic subjects using the Asthma Control Test questionnaire
- Urine pregnancy test, for females of childbearing potential
- Blood draw to collect samples for:
 - Peanut- and peanut-component specific IgE, total IgE, and peanut- and peanutcomponent specific IgG4 (immunoglobulin assays). The amount of blood to be taken for the immunoglobulin assays will be communicated from the central laboratory and included in the manual of procedures.
 - CBC, obtained with the same venipuncture as the blood draw for the immunoglobulin assays
 - Optional exploratory immune cell characterization by the Immune Tolerance Network (ITN). Note that these samples can be obtained with the same venipuncture as the blood draw for the immunoglobulin assays and CBC, but will require an addition volume of blood to be collected. Separate informed consent is required.

The amount of blood to be taken in total for the above assays (required immunoglobulin assays, required CBC, and optional immune cell characterization assays) will not exceed a total volume of 0.67 mL/kg in children, to a maximum of 50 mL, total, in 8 weeks. Blood draw should be collected in compliance with local laboratory guidelines and testing regulations.

- Skin prick test to peanut extract
- Review with subjects and parents or guardians teaching about food/peanut allergy according to the investigational site's established standards. This is to include at a minimum the following topics (some or all of which may be addressed in a comprehensive anaphylaxis action plan):
 - Recognition of an allergic reaction and of the symptoms of anaphylaxis
 - When and how to administer epinephrine via auto-injector

- Requirement to go to nearest emergency facility following use of epinephrine auto-injector
- Ways to minimize the risk of accidental exposure to peanut in, and outside of, the home (may be supplemented by referral to recognized food allergy organizations for access to additional learning materials)

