 - CBC, obtained with the same venipuncture as the blood draw for the immunoglobulin assays
 - Optional exploratory immune cell characterization by the Immune Tolerance Network (ITN). Note that these can be obtained with the same venipuncture as the blood draw for the immunoglobulin assays. Separate informed consent is required.

The amount of blood to be taken for the above assays (required immunoglobulin assays, required CBC, and optional immune cell characterization assays) be will not exceed a total volume of 0.67 mL/kg in children, to a maximum of 50 mL, total, in 8 weeks. Blood draw should be collected in compliance with local laboratory guidelines and testing regulations. (For subjects who are withdrawing prematurely from the study due to an AE, the blood draw at the Early Discontinuation Visit can be foregone if it was performed at the time that dosing with study product ceased.)

- Skin prick test to peanut extract
- Take home sachets (or capsules, as appropriate) for daily dosing until next visit (if enrollment in ARC004 does not happen at this visit)
- Monitoring for compliance
- Monitoring for AEs, including allergic symptoms (Section 6.7 and Section 7.2)

In addition to the procedures listed above, eligible subjects will have an Exit DBPCFC performed. Eligible subjects are those who tolerate 300 mg/d and are maintained at this dose for the approximately 24-week Maintenance Period. The Exit DBPCFC is to be conducted in accordance with PRACTALL guidelines, with the protocol-specified modifications, as described in Section 6.6.2.

Each subject participating in the study will be unblinded when he/she completes the Exit Visit procedures (including the Exit DBPCFC for eligible subjects), provided regulatory and IRB/EC approval for ARC004 have been received, the availability of IP for ARC004, and all major data queries for the subject have been resolved (Section 3.3). If this is not the case, the subject shall remain on blinded treatment until these requirements are satisfied. The subject should continue his or her maintenance visits (completed as unscheduled visits), every 30 days, and complete all protocol procedures at each visit until study completion and rollover to ARC004.

The end of the study is defined as the date of the last visit of the last subject.

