8.2.1 Optional Additional Blood Volume

Subjects who consent to participate in the optional substudy to characterize immune cell responses, conducted by the ITN, will have an additional volume of blood collected at the same time as the immunoglobulin assay blood draws (Section 8.1; full procedures will be provided in the manual of procedures). Participation in the substudy to characterize immune cell responses does not require an additional venipuncture.

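### Appendix 1 footnote h allows up to about 2.5 times more optional blood from a child than the visit sections allow for all blood together

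*Protocol*

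**What the plan says.** Two places in the protocol set a per-kilogram limit on blood volume.

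- **Appendix 1, footnote h.** It is attached to the schedule row "Optional extra vol. for ITNh", which is marked at Screening, the 300 mg end-of-up-dosing visit, Exit/Early Discontinuation and Unscheduled. It restricts the optional draw to subjects of at least 30 kg and sets the volume: "No more than 5 mL/kg may be drawn, up to a maximum of 50 mL total". It names no period over which the 50 mL is counted.
- **The visit sections.** Section 6.2 (screening) says the blood taken "will not exceed a total volume of 0.67 mL/kg in children, to a maximum of 50 mL, total, in 8 weeks". Section 6.3.4 (end of up-dosing) sets the same limit and lists what it covers: "required immunoglobulin assays, required CBC, and optional immune cell characterization assays) will not exceed a total volume of 0.67 mL/kg in children". Section 6.5 (exit or early discontinuation) repeats it for the same list of assays. Section 6.2.1 applies it to the post-challenge draw after screening, whose volume "will be such that it will not cause the total blood volume collected to exceed 0.67 mL/kg in children".

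Section 8.2.1 adds that ITN participants "will have an additional volume of blood collected at the same time as the immunoglobulin assay blood draws", so the optional volume comes on top of the required samples at one venipuncture. Section 6.4 (unscheduled visits and draws) provides for ITN samples when a subject declares an intention to stop dosing, and states no volume limit of its own.

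**The concern.** The footnote's ceiling for one component, the optional ITN blood, is higher for many children than the visit sections' ceiling for all components combined. Scope does not explain the difference, since Sections 6.2, 6.3.4 and 6.5 each place the ITN volume inside the 0.67 mL/kg total.

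The footnote also gives no weight-based protection. Its per-kilogram figure exceeds its own 50 mL cap at every weight it covers.

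This is a pediatric safety limit for an optional exploratory procedure. A site working from the schedule table alone could stay within footnote h and still exceed the limit the protocol sets for children.

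**Working it through.** The plan states no derived figure to reproduce, so the check compares the two ceilings directly.

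**Inputs**

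- Footnote h: 5 mL/kg, capped at 50 mL, weight at least 30 kg (Appendix 1).
- Visit text: 0.67 mL/kg in children, capped at 50 mL in 8 weeks (Sections 6.2, 6.2.1, 6.3.4, 6.5).

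**Formulas**, for body weight *w* in kg

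- Footnote ceiling, optional draw: min(5*w*, 50). Since 50/5 = 10 kg, the 50 mL cap binds from 10 kg upward, and so for every subject of 30 kg or more.
- Visit-text ceiling for a child, required plus optional: min(0.67*w*, 50). Since 50/0.67 = 74.6 kg, the cap binds only from about 75 kg.

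| Weight (kg) | 5 mL/kg before cap (mL) | Footnote ceiling (mL) | Visit-text ceiling (mL) | Ratio |
|---|---|---|---|---|
| 30 | 150 | 50 | 0.67 × 30 = 20.1 | 2.49 |
| 40 | 200 | 50 | 0.67 × 40 = 26.8 | 1.87 |
| 50 | 250 | 50 | 0.67 × 50 = 33.5 | 1.49 |
| 60 | 300 | 50 | 0.67 × 60 = 40.2 | 1.24 |
| 70 | 350 | 50 | 0.67 × 70 = 46.9 | 1.07 |
| 74.6 and above | 373 and above | 50 | 50 | 1.00 |

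The ratio is largest at the 30 kg minimum and falls to 2 at 50/(2 × 0.67) = 37.3 kg. The raw per-kilogram ratio, 5/0.67 = 7.5, applies to no covered subject because of the 50 mL cap. At 30 kg the uncapped figure is 150/50 = 3 times the footnote's own maximum.

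The comparison understates the gap. The visit-text total must also hold the required immunoglobulin and blood count samples, so less than 20.1 mL remains for ITN blood at 30 kg. The required volume is not given in the documents.

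**Where each limit appears.** Each scheduled visit marked on the ITN row has the 0.67 mL/kg limit in its own section. Unscheduled draws do not, because Section 6.4 is silent on volume. Footnote i also sends the ITN draw 5 to 10 days after the exit challenge to an unscheduled visit for subjects who do not enter ARC004. For these draws footnote h may be the only limit a site finds.

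**The case against.** The strongest reply is that both figures are upper limits and neither requires any volume. A site that follows the stricter visit text satisfies both, and that text appears wherever the scheduled draws are described. Actual volumes come from the manual of procedures and the central laboratory, and local guidelines apply as well. This stands for the scheduled visits, and it means overdrawing cannot be shown from these documents. It is weaker for unscheduled draws. Section 6.4 does say that a draw taken at the decision to stop dosing replaces the Section 6.5 draw, so a careful reader might carry the limit across, but Section 6.4 does not state it.

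The footnote's 50 mL could also be read as the same overall cap used in the visit text, not as a cap on the optional draw alone. That would weaken the point about adding it to the required draw, but the per-kilogram conflict would remain.

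The 2.5-fold figure is the extreme, found only at 30 kg. Above about 37 kg the ratio is below 2. Children under 30 kg are excluded by the footnote, and adults are outside the 0.67 mL/kg limit.

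Finally, many of the draws may be past. Section 9.4 says enrollment was complete at Amendment 4, which SAP Section 2.4 dates to 31 July 2017. SAP Section 1.1 places the first unblinding at about December 2016, and protocol Section 6.12 expected enrollment to finish before the first exit. If that held, more than 30 weeks had passed against a nominal 20 and maximum 40 weeks of up-dosing, so most end-of-up-dosing draws would be over. Exit and unscheduled draws could remain.

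**Conclusion.** The concern holds. Footnote h and the visit sections set incompatible pediatric blood limits, and the footnote's is the looser by up to 2.49-fold, at 30 kg. The conflict covers consenting children from 30 kg to about 75 kg. How many there are is not stated.

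The size rests on reading both figures as ceilings and on applying the 50 mL cap and the 30 kg minimum as written. It measures the gap between permitted volumes, not blood actually taken. The matter is one of subject protection and internal consistency. Efficacy, power and type I error are untouched. It should be corrected, because the wrong figure may be the only one a site sees for unscheduled draws and because the correction is simple.

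**What to change.** Replace the volume limit in footnote h with the protocol's own pediatric limit. Suggested wording:

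> Optional blood draw for subjects ≥ 30 kg only. No more than 0.67 mL/kg in children, maximum 50 mL in 8 weeks, counting all required and optional draws.

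Because the row is also marked under Unscheduled, this one edit supplies the missing limit for those draws too. Send sites a short clarification so that remaining exit and unscheduled draws follow the corrected figure.

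The cost is one footnote and one notice. Endpoints, analysis, power and blinding do not change.
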